8.2 Data Analyses ^{ct.gov}	26
8.2.1 General Approach	26
8.2.2 Primary Outcome	26

8.2.3 Secondary Outcome.....	Error! Bookmark not defined.
9 Regulatory, ethical and study oversight considerations.....	27
9.1 Informed Consent Process ^{eRsrch}	27
9.2 Confidentiality and Privacy ^{eRsrch}	27
9.3 Future Use of Stored Specimens and Data	27
9.4 Data Handling & Record Keeping	27
9.4.1 Quality Assurance & Quality Control	27
9.4.2 Training	28
9.4.3 Protocol Deviations	29
9.4.4 Monitoring.....	29
10 COMMITTEES	29
11 REFERENCES.....	29
12 APPENDICES.....	Error! Bookmark not defined.

PROTOCOL SUMMARY^{CT.GOV}

Title:	Alcohol Screening and Pre-operative Intervention Research (ASPIRE) study
Study Description:	The present study aims to conduct a randomized pilot test of two intervention conditions for risky alcohol use prior to elective surgery: Brief Advice and Health Coaching. This study builds on existing research indicating that moderate alcohol use (>2 drinks/day) prior to surgery increases the risk of postoperative morbidity, and heavy alcohol use (>4 drinks/day) increases the risk of postoperative mortality. This study will enhance our knowledge of how health coaching can influence problematic alcohol use, improve patient health, bolster hospital outcomes, and reduce the cost of postoperative care.
Outcomes:	The primary goal of this trial is to develop and examine the initial efficacy and acceptability of the health coaching intervention relative to brief advice with regards to reducing alcohol use prior to surgery. The primary outcome is change in alcohol use (average weekly drinking) and the secondary outcome is acceptability (perception of the interventions personal relevance). This trial has the following hypotheses but is likely under-powered to detect statistically significant differences.
	Hypothesis 1: Relative to the Brief Advice group, the Health Coaching group will experience greater reductions in average monthly alcohol use (quantity by frequency) based on the time line follow back.
Intervention Information:	The health coaching session will include two in-person individual sessions that will provide information about alcohol use reduction before and after surgery, delivered in a motivational interviewing format. Patients will have the choice of in-person or virtual meetings (via encrypted, university-supported virtual meeting platform). Brief advice will include a single 10-minute individual session of alcohol use reduction advice delivered virtually via encrypted, university-supported virtual meeting platform. The objective of both interventions is to motivate participants to maintain abstinence from alcohol for 4 weeks before and 6 weeks after surgery.
Study Population:	The study population will be approximately 90 elective or semi-elective surgical patients recruited from Michigan Medicine pre-operative clinics. Patients will be 18 to 75 years old and can identify as any gender or race/ethnicity.
Locations: ^{erSch}	Patients will predominantly be recruited over the phone and online, after being identified by medical chart review. They may also be recruited in-person from outpatient Michigan Medicine clinics that evaluate patients for surgical candidacy at numerous locations

including, but not limited to, Taubman Clinic, Domino's Farms, West Ann Arbor, and Northville.

Estimated Study Start Date: *March 1st, 2019.*

Study Duration: *Two years and four months.*

1 BACKGROUND & RATIONALE

1.1 Background^{ERSCH}

Pre-operative alcohol use is one of the most common surgical risk factors and is one of the few that is modifiable¹. A meta-analysis of 55 studies (combined N = 1,234,923) indicates pre-operative alcohol consumption (> 2 standard drinks/day) is associated with an increased risk of various postoperative complications including general morbidity, infections, wound complications, pulmonary complications, prolonged hospital stay, and admission to intensive care unit². Heavier alcohol consumption (> 4 standard drinks/day) is associated with increased risk of postoperative mortality. These risks are not specific to certain surgeries or subpopulations, they are evident across all surgeries² even after controlling for covariates such as gender and past year smoking status^{3,4}. Importantly, short-term abstinence prior to elective surgery can reduce postoperative risks in as little as four to eight weeks (or less)⁵. Every additional point scored on the AUDIT-C increases the expected number of post-surgical complications by 29%⁶. Pre-operative alcohol use is linked to longer hospital stays, admission to the intensive care unit (ICU), and increased probability of returning to the operating room⁷. All told, pre-operative risky drinking leads to numerous health consequences for individuals and increased costs to the healthcare system and society.

There is a scarcity of treatment and prevention research focused on pre-operative risky drinking. This is striking given the that the vast majority of hospital patients, including surgical inpatients, accept alcohol screening and BMI when it is offered⁸⁻¹⁰. Brief interventions are a recommended way to reduce risky drinking prior to surgery^{5,6}; There remains a critical need for research to develop and evaluate the impact of pre-operative brief interventions on alcohol use and postsurgical outcomes. This study aims to take the initial steps to address this research gap.

1.2 Study Rational

There has been a call for additional research and development of behavioral interventions for alcohol use during the pre-operative period. However, these practice and research recommendations have not been implemented. At this time, there is a great need for research to identify and reduce alcohol use prior to elective surgery in order to improve patient health outcomes and reduce unnecessary healthcare utilization and costs. Therefore, this study will conduct a randomized pilot trial to evaluate initial efficacy of two interventions aimed at reducing alcohol use. Pre-operative patients (N = 90) will be recruited from University of Michigan Healthy System clinics and randomized to receive either a 2-session health coaching intervention (n = 45) or brief advice (n= 45).

2 OUTCOMES^{CT.GOV;ERSCH}

2.1 Primary Outcome

The primary goal of this trial is to test initial efficacy of health coaching relative to brief advice. The primary outcome that this trial is powered to detect is change in alcohol use (defined as average weekly drinking) from baseline to one month follow-up (pre-operative outcome) and from baseline to the four month follow-up (post-operative outcome) in the Health Coaching condition relative to the brief advice condition.

2.2 Secondary Outcomes

The secondary outcome of this trial is acceptability of the two interventions. Acceptability is defined as the extent to which participant's perceive the intervention as personally relevant. We will consider the interventions acceptable based on post-intervention evaluations. Specifically, interventions will be considered 'acceptable' if the average acceptability rating reaches a threshold of 4 or more on a 5-point Likert scale.

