Health Coaching will consist of two (2) sessions beginning four (4) weeks before the patient's surgery. The sessions will be spaced two (2) weeks apart to accommodate patient response to the intervention. Each Health Coaching session will last approximately 50 minutes. During the Health Coaching sessions, a trained research team member will discuss alcohol use and health during the pre-operative period by using motivational enhancement therapy techniques to improve the patient's motivation to change. Additionally, the research team will provide the patient with alcohol use resources during the Health Coaching sessions. If a participant cannot complete all study activities during one visit, we will allow participants to set an appointment to complete these activities within three days. Follow-up surveys will take place at one-week prior to surgery and one-month post-surgery. A staff member at the pre-operative clinic will also give patient's an infographic about alcohol and surgical health during their clinic visit approximately two weeks prior to surgery.

Delivery: All Health Coaching sessions will be delivered by a member of the research team trained in motivational interviewing. The research team will give patients the option of in-person meetings, or virtual meetings via encrypted, university-supported virtual meeting platform . The Health Coaching sessions will be audio-recorded for quality assurance purposes encrypted, university-supported virtual meeting platform with HIPAA-compliant conferencing services will be used for the videoconferencing or phone meetings. In-person meetings will take place at UM or a building within the UMHS, or a mutually agreed upon location within the community. The infographic will be provided at the patient's pre-existing pre-operative clinical visit.

Intervention Targets (mechanistic and clinical outcomes):

The goal of the pilot trial is to assess the initial efficacy of health coaching relative to brief advice and determine the acceptability and feasibility of both interventions. This study is underpowered to assess mechanisms of change.

Supportive Theories

Supportive theories include social learning theory and motivational interviewing

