5.4 Intervention Discontinuation

Withdrawal of consent will result in true study discontinuation with no interview or assessment performed. Any information collected before withdrawal will be kept as part of the subject's record. The study will document the patient's reason for withdrawal, if available, to track for study purposes.

Patients can also be withdrawn by the study if they become ineligible after consent. These reasons include (1) surgery cancelation or rescheduling with a greater than 6-month delay, (2) demonstrating substantial cognitive impairment at two time points as evidenced by lack of orientation to person, place, or time or lack of ability to repeat back and answer questions; or (3) displays or shows evidence of psychotic symptoms, (4) fails to follow instructions of the researchers.

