5.5.1 Overall compliance

A participant will have completed the brief advice intervention after receiving the 10-minute brief advice session. A participant will complete health coaching after receiving

the two 50-minute health coaching sessions. We will track intervention completion in REDCap.

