6 STUDY PROCEDURES^{ERSCH}

For Phase 3 we will conduct a randomized pilot trial test of Health Coaching and Brief Advice interventions to reduce alcohol use prior to elective surgery. The goal of the pilot trial is to assess the initial efficacy of Health Coaching relative to the Brief Advice Intervention and determine initial acceptability, feasibility, and fidelity of both conditions. Participants have a choice of intervention modality and they will either take place in-person or as a virtual meeting using an encrypted, university-supported virtual meeting platform. The in-person meetings will take place at either the Rachel Upjohn Building, in MCRU research space, or at a building within UM or UMHS, or a mutually agreed upon location within the community. If a participant cannot complete all study activities during one visit or virtual visit, we will allow participants to set an appointment to complete these activities within three days. This study has one baseline assessment. Follow-up surveys will take place at one-month post-baseline (Follow up 1; one week pre-surgery) and at four-months post-baseline (Follow-up 2; 3-months post-surgery).

Randomization

Participants will be urn randomized to study condition using computerized random number generator. Groups will be balanced based on gender.

Assessment and Measures

Baseline assessment will take place at least four weeks prior to surgery. The baseline assessment will take approximately 40 minutes to complete. Thus, the first appointment will take up to 120 minutes for those randomized to health coaching (15 minutes to

review the consent form; 40 minutes for baseline assessment; 50 minutes for the intervention; 10 minutes for the post-intervention feedback; and 5 minutes to provide the incentive) or 75 minutes for those assigned to receive brief advice (15 minutes to review the consent form; 40 minutes for baseline assessment; and 10 minutes for the brief advice intervention and 10 minutes for intervention feedback evaluation).

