Drug use assessments include the NIDA modified Alcohol, Smoking, and Substance Involvement Screening Test (ASSIST)¹⁸ and the Current Opioid Misuse Measure (COMM-8)¹⁹. Health and functioning assessments include Patient-Reported Outcomes Measurement Information System (PROMIS-29)²⁰.

Other measures related to treatment mediators and moderators include assessments of Social Support^{21,22}, Health Service Utilization^{23,24}, Pre-operative Surgical Anxiety²⁵, knowledge of surgical risk factors, pain management practices, and healthcare surgical

risk assessment.

Alcohol and Drug Use biomarkers. On the day of surgery, a urine and blood sample will be collected and alcohol and drug screening labs ordered through the electronic health record. The lab order will include ethyl glucuronide, phosphatidylethanol, and gas chromatography. The results will be shared with the research team and not affect the patient's current surgical candidacy. This measure is exploratory.

Medical Chart Review. The research team will extract and analyze de-identified data from patient's medical records to evaluate the impact of the alcohol brief intervention on perioperative morbidity and mortality. No HIPAA identifiers will be collected from the patient medical record, except dates of treatment and dates of death (if applicable). The dataset will not be linked to patient identifying information. This measure is exploratory.

Post-Intervention Assessment. Participants will also complete brief assessments following intervention completion regarding 4 domains: (1) perceived clinical usefulness (2) personal relevance, and (3) level of engagement, and (4) areas in need of adaptation. The secondary outcome (perception of interventions personal relevance) is gathered here.

Qualitative Exit Interview: After the study is complete (N = 20) participants that indicated willingness to be re-contacted (in consent form) will be asked to complete an exit interview (open-ended researcher-delivered questions) about why they did or did not change their alcohol use, and what the role of the intervention was in that decision making process. The purpose is to further refine the intervention conditions for further development and dissemination. This measure is exploratory.

Intervention Conditions

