6.2.5 Outcome Assessments

The change alcohol use and acceptability assessments will occur at three times throughout the study: baseline, one-month post-baseline, and four-months post-baseline. See List of Study Activities Table. We will verify alcohol and drug use reports through a blood draw and urine drug screen conducted on the day of surgery that will undergo lab testing for drug/alcohol biomarkers.

Qualitative Interviews

A total of 20 patients, 10 from each intervention condition, will be selected (based on response vs. non-response to intervention. Response is defined as an alcohol use reduction of greater than one standard deviation from the mean between baseline and final follow-up. Non-response is defined as any increase in alcohol use between baseline and final follow-up or no change in alcohol use. These participants will be asked to complete exit interviews regarding their experience. Qualitative interviews with patients occur during a single interaction with research staff. Qualitative interviews will be audio recorded. We will initially focus our patient interviews on what factors led to change or lack of change in alcohol use, and how the intervention played a role in these changes, and how the intervention could be improved.

6.2.6 *Withdrawal*

If subjects withdraw or decline to finish treatment, we will make every effort to gather primary outcome data at regularly scheduled follow-ups. We will also query for an adverse event over the phone or in person. For subjects who wish to withdraw completely from the study, we will make every effort to collect the data as soon as possible – i.e. when the individual lets you know of their decision to withdraw. We will continue to use data that was obtained prior to withdrawal date unless the participant asks for it to be destroyed. The data will be kept secure until it is destroyed.

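### Does the acceptability threshold leave out Health Coaching patients who stop after the first session?

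*Combined protocol and SAP*

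**What the plan says.** Acceptability is the only secondary outcome. Section 2.2 defines it as perceived personal relevance, takes it from evaluations made after the intervention, and sets the criterion that "the average acceptability rating reaches a threshold of 4 or more on a 5-point Likert scale". It does not mention completers.

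The timing of the rating is given in several places:

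- **Section 6, Post-Intervention Assessment:** "Participants will also complete brief assessments following intervention completion regarding 4 domains". This paragraph also says the secondary outcome is collected here.
- **Section 5.5.1:** Health Coaching is complete after "the two 50-minute health coaching sessions. We will track intervention completion in REDCap"; Brief Advice is complete after its one session. Section 5 adds, for Health Coaching, "The sessions will be spaced two (2) weeks apart".
- **Section 6, Assessment and Measures:** the first Health Coaching appointment includes "50 minutes for the intervention; 10 minutes for the post-intervention feedback; and 5 minutes to provide the incentive". The Brief Advice appointment includes "10 minutes for the brief advice intervention and 10 minutes for intervention feedback evaluation".
- **Table 1 (Section 6.1):** one row covers interventions and their evaluations, marked at Baseline and at Week 3.
- **Section 6.2.2:** an assessment of acceptability and relevance follows the Brief Advice and Health Coaching sessions.
- **Section 6.2.5:** alcohol use and acceptability share one timetable of baseline, one month and four months.

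Section 8.2 contains no analysis of the secondary outcome.

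**The concern.** If a rating exists only once an intervention is complete, and completion of Health Coaching means two sessions two weeks apart, a patient who does not return for the second session contributes nothing to the Health Coaching mean. Failing to return may itself signal low personal relevance, so the score would rise through the loss of its least satisfied patients. Brief Advice has no such filter, because its session and its feedback fall in the same appointment. One cut-off of 4 would then be applied to completers in one arm and to all starters in the other.

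The follow-up rules seem to offer no remedy. Section 6.2.6 says "If subjects withdraw or decline to finish treatment, we will make every effort to gather primary outcome data at regularly scheduled follow-ups", which names only the primary outcome, and Section 5.4 says "Withdrawal of consent will result in true study discontinuation with no interview or assessment performed". Section 8.1 says the sample size was chosen mainly to support conclusions on feasibility and acceptability, so a flattering Health Coaching score could carry into the design of the later full trial.

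**Working it through.** **Step 1. Is a rating scheduled after session 1?** The plan's own time budget can be checked.

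- Health Coaching, first appointment: 15 (consent) + 40 (baseline) + 50 (intervention) + 10 (feedback) + 5 (incentive) = 120 minutes, the stated total.
- Brief Advice: 15 + 40 + 10 + 10 = 75 minutes, the stated total.

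Both totals reproduce only with the ten minutes of feedback included; without them the first would be 110 minutes. The first Health Coaching appointment holds one 50-minute session, and the text calls that session the intervention and what follows it post-intervention feedback. In Section 6, then, a rating after the intervention can mean a rating after a single session.

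**Step 2. Do the other timing passages agree?** In Table 1, Baseline is Week 1 and the next mark is Week 3. That matches two sessions two weeks apart, each with an evaluation. Section 6.2.2 speaks of sessions in the plural. Section 6.2.5 is the outlier: Table 1 shows no intervention evaluation at Week 5 or Week 18, so its sentence reads as a slip that gave acceptability the alcohol-use timetable.

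**Step 3. How large could the effect be if only end-of-course ratings counted?** The threshold has no stated derivation, SD or power, so there is no figure to reproduce. The inputs are:

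- 45 patients per arm (Section 1.2) and a 1-to-5 scale (Section 2.2, taking 1 as the lowest point);
- the number *n* attending session 2, which the documents do not give. I take 36, 40 and 43 of 45. The 36 borrows the 80% retention target of Section 6.2.3, which concerns study follow-up, not session attendance.

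With a completer mean of exactly 4.0, the all-starter mean lies between [4*n* + 1(45 − *n*)]/45 and [4*n* + 5(45 − *n*)]/45.

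| Attending session 2 | Lowest | Highest |
|---|---|---|
| 36 of 45 | (144 + 9)/45 = 3.40 | (144 + 45)/45 = 4.20 |
| 40 of 45 | (160 + 5)/45 = 3.67 | (160 + 25)/45 = 4.11 |
| 43 of 45 | (172 + 2)/45 = 3.87 | (172 + 10)/45 = 4.04 |

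The lowest values need every non-completer to give the minimum score. If nine non-completers averaged 3, the first row would give (144 + 27)/45 = 3.80.

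**Step 4. When would the verdict flip?** Suppose completers average 4.2. The all-starter mean falls below 4 when the stoppers' mean is below [4 × 45 − 4.2*n*]/(45 − *n*).

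- *n* = 36: (180 − 151.2)/9 = 3.2
- *n* = 40: (180 − 168)/5 = 2.4

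If stoppers rate the same as completers, nothing changes at any attendance. Pass probabilities would also need an assumed SD and true mean, so I give none.

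**The case for a change.** The strongest case for acting is that no passage settles the matter. The Post-Intervention Assessment paragraph is the only one that says where the secondary outcome is gathered, and it speaks of completion. The first-appointment feedback is not said to contain the relevance item. Table 1 is headed as an example from a template, and its Baseline mark would be needed anyway for session 1 and for Brief Advice. The plural in Section 6.2.2 fits either each session or the whole course. The contents list a Section 8.2.3 on the secondary outcome, but the text has none. Even with two ratings in hand, the plan does not say whether the first, the last or both enter the mean.

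Much of this stands. The passages conflict, and the rating to be averaged and the denominator are unwritten. What does not stand is the stronger claim that early stoppers cannot lower the Health Coaching score. That requires reading completion in Section 6 through the compliance definition in Section 5.5.1 and setting aside the timetabled feedback. Nor is recovery ruled out: for complete withdrawal, Section 6.2.6 also promises an effort to collect data when the patient announces the decision, without limiting this to the primary outcome. That sits awkwardly with Section 5.4, but it is not silence.

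**Conclusion.** The selection effect is real only under one reading, and not the most natural one. Under the timetable in Section 6, Table 1 and Section 6.2.2, a patient who leaves after session 1 has been asked for a rating, and an analyst who uses the ratings collected gets no wrong result. The remaining gap is a missing definition. It can be filled sensibly by averaging over everyone who attended a session and stating how many were rated. Completion is tracked in REDCap, so non-attendance at session 2 will be visible beside the score.

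The stakes are modest. Each intervention is judged descriptively against 4, with no test, in a pilot whose hypothesis testing Section 8.1 calls exploratory. Fixing one estimate in advance brings no clear gain: pooling session-1 with session-2 ratings mixes half and full exposure, while a completer mean describes those who received the whole intervention. Either is defensible if labelled. The range of 3.4 to 4.2 rests on an assumed 36 of 45 attending, and at 43 of 45 it narrows to 3.87 to 4.04. No change to the plan is called for. This conclusion rests on the first-appointment feedback covering personal relevance, which the documents imply but do not state.
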